14.3. Baseline and Demographic Characteristics

Baseline and demographic characteristics will be summarized. Continuous variables will be summarized using descriptive statistics such as mean, median, minimum, and maximum, while gender, race, and other categorical variables will be provided using frequency tabulations. Medical history data will be summarized using frequency tabulations by the Medical Dictionary for Regulatory Activities (MedDRA) system organ class and preferred term.

14.4. Subject Disposition

Subject disposition (analysis population allocation, entered, discontinued, along with primary reason for discontinuation) will be summarized using frequency and percent. A summary of subjects enrolled by site will be provided. Protocol deviations will be summarized using frequency tabulations.

14.5. Safety Analysis

Safety analysis will be based on the Safety Population. Descriptive statistics will be provided for AEs, vital sign measurements, physical examination findings, clinical laboratory test results, infusion site assessments, and concomitant medications and procedures.

AEs observed will be classified using the MedDRA classification system (MedDRA version 23.0). The severity of the toxicities will be graded according to the NCI CTCAE, version 5.0 whenever possible. Adverse events will be summarized by MedDRA system organ class and preferred terms, and separate tabulations also will be produced for related adverse events, SAEs, discontinuations due to adverse events, and events of at least Grade 3 severity. A summary of the number and severity of CRS AEs will also be produced. AEs will be summarized by study period for those events that occur during the study periods.

Vital signs data and laboratory data will be tabulated for changes over time.

Laboratory parameters will be summarized for changes across study using descriptive statistics including shifts relative to CTCAE criteria for laboratory abnormalities. Laboratory measures will also be compared with their corresponding normal ranges, and the incidence of abnormally high and abnormally low laboratory values will be summarized.

Graphical displays may be provided where useful in the interpretation of results.

14.6. Efficacy Analysis

Phase I efficacy data will be summarized by descriptive analyses. The efficacy endpoints used in the lack of efficacy tests is the responses at Day 15 of the clinical improvement by OSCI. If efficacy is not established in 2 out of the 14 subjects, the study will be terminated. If efficacy is noted in 2 or more subjects, the study will move forward to the Phase II portion.

Efficacy endpoints are defined in [Section 6.9](#).

Phase II efficacy data will be summarized by descriptive analyses. The efficacy endpoints used in the lack of efficacy tests is the responses at Day 15 of the clinical improvement by OSCI. If efficacy is not established in 2 out of the 14 subjects, the study will be terminated. If efficacy is noted in 2 or more subjects, the study will move forward to the Phase III portion.

No interim analysis will be implemented in this study.

14.8. Sample Size and Power Considerations

Phase I:

Fourteen (14) subjects will be treated by CYNK-001 in the Phase I portion. Based on clinical judgement for this coronavirus disease and the current treatment status, this sample size is

appropriate to evaluate the safety of CYNK-001, and to evaluate the lack of efficacy before starting Phase II portion. This number is not based on hypothesis testing and power calculation.

Phase II

14.9. Subject Replacement

Subjects will not be replaced.

14.10. Study Stopping Rules

Phase I of the study:

a. Safety Stopping Rules:

In addition to the evaluation of vital signs, performance status, a Consultation with the Medical Monitor is required prior to each CYNK-001 infusion if there is:

- an increase in supplemental oxygen of greater than or equal to 50% from baseline (for first CYNK-001 infusion) or from level at prior CYNK-001 infusion (for second and third CYNK-001 infusion) resulting in oxygen use of greater than 8L.

-or-

- a change in the mode of supplemental oxygen delivery with the intention to deliver oxygen more efficiently.

The Medical Monitor will escalate to the Sponsor clinical and safety team as appropriate per GCP guidelines to advise if a subject who is experiencing rapid worsening of disease should proceed to first or subsequent CYNK-001 infusion.

b. Study Stopping Rules:

- During Phase I, 3 subjects will be initially monitored for any potential DLTs until 24 hours after the final dose given to the 3rd subject. If any DLTs occur, the DMC will be convened. Study will proceed to enroll the remaining 11 subjects if it is deemed safe in the first 3 subjects. For the remaining 11 subjects, DMC will be convened if the safety stopping rule which is defined as death in any of the subjects irrespective of relatedness to the product is met. Overall, in case of 2 out of the 6 subjects had experienced DLTs in the Phase I portion of this study, the DMC will be convened for safety evaluation.

- The study will be stopped, and DMC will be convened, if death in any of the 14 subjects had occurred by Study Day 15 from the first dose of CYNK-001 infusion irrespective of relatedness to CYNK-001. If no such events have occurred in all 14 subjects, it is deemed safe to proceed to Phase II of the study.
- All other serious adverse events assessed as “Related to product” will be tracked and sent for DMC review and recommendation but will not trigger the study to be stopped unless recommended by the DMC Chair.
- Worsening of a condition in any subject will be tracked and sent for DMC review and recommendation but will not trigger the study to be stopped unless recommended by the DMC Chair.

b. Efficacy (Futility) Stopping Rules:

By Day 15 of CYNK-001 infusion in the Phase I, the study may stop for futility if there is less than 2 subjects with clinical improvement of at least one “Patient State” category as defined by the OSCI ([Appendix D](#)).

If at least 2 out of the 14 subjects by Day 15 demonstrated efficacy in the Phase I portion of the study, the study will move forward to the Phase II.

Phase II of the study:

- The study will be stopped, and DMC will be convened: if death had occurred by Study Day 15 of CYNK-001 infusion irrespective of relatedness to the product.
- DMC will be convened at midpoint (after 18 subjects have received treatment) during this portion of the study to evaluate safety for adverse event of interest such as shock, ARDS, and death in the treatment group versus the control group.
- All other serious adverse events assessed as “Related to product” will be tracked and sent for DMC review and recommendation.
- Worsening of a condition in any subject will be tracked and sent for DMC review and recommendation but will not trigger the study to be stopped unless recommended by the DMC Chair.

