5.4. Study Endpoint Descriptions

Table 2: Study Endpoints

Endpoint	Name	Description	Timeframe
Phase 1			
Phase 1 Primary	Safety	Frequency and severity of adverse events, changes in vital signs, laboratory assessments, Performance Status assessment, and immunological and inflammation assessments.	DLTs assessed from Study Day 1 through Day 28
Futility Check for go/no go decision to move to Phase 2:		Efficacy as measured by clinical improvement by OSCI. At least 2 out of 14 subjects must achieve at least 1 "Patient State" category improvement in Ordinal Score (OSCI)	Study Day 15
Phase 2			
Phase 2 Primary	Time to clinical improvement by OSCI	Time to clinical improvement measured by OSCI	Study Day 28
Phase 2 Secondary	Clinical status by OSCI	Ordinal scale by OSCI	Study Day 28
	Rate of clinical improvement by OSCI	Proportion of subjects who achieved clinical improvements by OSCI	Study Day 28
	Time to clinical improvement by NEWS2	Time to clinical improvement measured by NEWS2 Score	Study Day 28
	Rate of clinical improvement by NEWS2	Proportion of subjects who achieved clinical symptom improvement by NEWS2 Score	Study Day 28
	Rate of clearance of SARS-CoV-2	Proportion of subjects with clearance of SARS-CoV-2 from mucosal specimens (nasopharyngeal swab, oropharyngeal swab if available)	Study Day 28
	Time to clearance of SARS-CoV-2	Clearance of SARS-CoV-2 by rRT-PCR testing of mucosal samples (nasopharyngeal swab, oropharyngeal swab if available); negative results should be confirmed by same sample type at least 24 hours after the first negative result	Study Day 28

	Time to pulmonary clearance	Time to disappearance of virus from LRT specimen where it has previously been found (induced sputum if available, endotracheal aspirate if available)	Study Day 28
	Rate to pulmonary clearance	Proportion of subjects who had disappearance of virus from LRT specimens where it has previously been found.	Study Day 28
	Duration of hospitalization	Duration of hospitalization from time from hospitalization to medical discharge	Study Day 28
	Supplemental oxygen-free days	For subjects requiring supplemental oxygen, days with supplemental oxygen-free days	Study Day 28
	Proportion of subjects requiring ventilation	Proportion of subjects who need invasive or non-invasive ventilation	Study Day 28
	SOFA Score	Sequential Organ Failure Assessment (SOFA) score	Study Day 28

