6.3. Dose Limiting Toxicity (DLT) Definition

Known pathologies associated with COVID-19 will be carefully considered and differentiated from potential CYNK-001-related effects in order to identify CYNK-001 related toxicities. Adverse events occurring up to Day 28 from the first dose of the CYNK-001 infusion will be included in the dose-limiting toxicity (DLT) determination.

A DLT is defined as the development of any new (not pre-existing) events:

- Grade 4 or 5 event in any organ system
- Grade 4 > 24 hour (Due to known organ damage associated with the COVID-19) in the following organ systems:
 - Cardiac
 - Pulmonary
 - Hepatic
 - Renal
 - Central Nervous System (CNS)
- Grade 3 or above allergic reaction that is suspected to be related to CYNK-001.
- Grade 3 or above GvHD event occurring within the first 28 days following CYNK-001 infusion (to Study Day 28).
- Grade 3 or above CRS event occurring within the first 28 days following the first CYNK-001 infusion (to Study Day 28).

All above events to be identified in discussion with the clinical study Medical Monitor and reportable to Drug Safety.

The events will be assessed for the first 3 subjects in Phase I and per the study stopping rules for the remaining subjects. Any such findings will be forwarded to the DMC for recommendation, review and confirmation as to whether or not the maximal tolerated dose (MTD) has been exceeded. If the MTD is confirmed by the DMC, no further CYNK-001 administration will occur within that dose level or at any higher dose level. For the remaining 11 subjects, DMC will be convened if the safety stopping rule is met. Overall, in case of 2 out of the 6 subjects had

experienced DLTs in the Phase I portion of this study, the DMC will be convened for safety evaluation.

During Phase II portion of the study, DMC will be convened at midpoint (after 18 subjects have received treatment) to evaluate safety for adverse event of interest such as shock, ARDS, and death in the treatment group versus the control group.

MTD is defined as the highest CYNK-001 dose level wherein it was deemed safe per the defined stopping rules or if the DMC recommends stopping the study due to DLTs suspected to be related to CYNK-001.

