14.11. Other Topics

14.11.1. Dose Limiting Toxicity (DLT)

For the purposes of DLT assessments for the Phase I portion of the study, AEs will be collected up to Day 28 post first dose of CYNK-001 infusion. Please refer to [Section 6.3](#) for definitions.

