14.11.2. Data Monitoring Committee (DMC)

A DMC will monitor the safety and efficacy information to ensure subject safety in accordance with a separate charter. The DMC may be comprised of external members who may not be involved in the day-to-day activities of the CYNK-001 study team but will be physicians and/or Clinical Research Experts with experience treating coronavirus infections and/or clinical trial involvement with this specific subject population. The DMC will recommend whether dose de-escalation is required, whether modifications to the protocol design are necessary or whether to end dosing and/or further enrollment to the study is required. The DMC will make their determinations based on available clinical data. The decisions of the DMC will be documented in meeting minutes.

An initial DMC meeting to introduce the DMC members to the Celularity study team, relevant other parties and provide an overview of the overall study plan with applicable documentation will be conducted. The DMC will be convened for subsequent meetings:

- Upon completion of 24 hours after the final dose was provided to the 3rd subject in the Phase I portion of the study to evaluate the safety data.
- Upon an event that met the safety study stopping rules in both Phase I and Phase II of the study ([Section 14.10](#)).
- After Day 15 of the final subject treated in the Phase I portion of the study is complete, DMC will meet for review of safety and efficacy data and to recommend moving forward with the Phase II portion of the study.
- Upon completion of the study.
- In the event that during the course of the Phase I or Phase II portions of the study, even if a single subject experiences an event listed below, the DMC Chair will be notified within 24 hours of the sponsor being informed. The DMC chair may review the case and if deemed necessary request that a meeting be convened to evaluate the event. If specified, the site may be placed on investigational medicinal product (IMP) treatment hold until the event is investigated.
 - A DLT event during 28 days from first dose of CYNK-001 infusion (to Study Day 28).
- When the DMC chair requests an ad hoc meeting (e.g., when an Urgent Safety Measure requires).
- Closed session may be held during the DMC meeting per request from the DMC Chair.

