- Participation of treating investigators in the DMC meetings is optional. DMC may request treating investigators to attend DMC meeting and provide additional information for subject under review.
- Data outputs for review should be provided to the DMC via email at least 2 weeks prior to scheduled meeting.

At a minimum, the scope of the meeting/suggested agenda for subsequent DMC meetings is as follows:

- a. Overview of current study enrollment status including but not limited to, recruitment, ineligibility rate and site status.
- b. Overview of subject status including but not limited to, baseline characteristics, safety/adverse event profile and known subject outcomes.
- c. Cumulative data for all subjects enrolled into the study, including safety and efficacy information.
- d. Suggestions for modifications to any of the documents listed below
 - a. Format of interim reports to the DMC
 - b. Method and timing of the delivery of the report to the DMC members prior to the meeting
 - c. Protocol
 - d. Master informed consent document
 - e. Case report forms
 - f. Other important study documents
- e. Conclusions/Recommendation Rationale for moving forward with the study
- f. In the event of an ad hoc meeting, the scope of the information will be defined by the event that lead to the meeting request (e.g., Urgent Safety Measure)

The Sponsor will take appropriate action based upon the recommendations of the DMC and this will be communicated to the Investigator. The Investigator will be responsible for notifying their IRB/EC.

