2.3 Exploratory Objectives

Exploratory objectives include detection of SARS-CoV-2 via rRT-PCR in various specimen types, cytokine and chemokine measurement, and immune monitoring, alloreactivity measurement.

3. Study Design and Procedures

The study includes two phases with safety and efficacy evaluation between phases to determine the implementation of phase II study.

In the Phase I portion, a total of 14 subjects will be enrolled to assess the safety and efficacy of CYNK-001. To evaluate the safety for potential dose limiting toxicities (DLTs), this phase will enroll 3 subjects initially treated with CYNK-001. If any DLT is observed in the first three subjects, the DMC will be convened for a recommendation. The safety data for these 3 subjects will be evaluated 24 hours after the final dose was provided to the 3rd subject. If deemed safe, the remaining 11 subjects will be enrolled and monitored per the safety stopping rule until Day 15 after the first CYNK-001 infusion.

The starting dose is 150×10^6 cells on Day 1 followed by 600×10^6 cells on Days 4 and 7. The dose limiting toxicities (DLTs) will be evaluated for 28 days following the first dose of the CYNK-001 infusion (Day 1).

MTD is defined as the highest CYNK-001 dose level wherein it was deemed safe per the defined stopping rules or if the DMC recommends stopping the study due to DLTs suspected to be related to CYNK-001. In Phase I, any DLT finding will be forwarded to the DMC for recommendation, review and confirmation as to whether or not the MTD has been exceeded. If the MTD is confirmed by the DMC, no further CYNK-001 administration will occur within that dose level or at any higher dose level.

A de-escalation Dose level -1 will be initiated based on the study stopping rules and DLTs. Dose de-escalation is defined as reducing the frequency of doses by providing doses only on Days 1 and 7 due to potential safety concerns per the DMC recommendation. Once CYNK-001 is deemed safe per the stopping rule and if efficacy is established in at least 2 out of the 14 subjects by Day 15 of the CYNK-001 infusion, it will trigger the initiation of the Phase II of the study. If efficacy has not been demonstrated, the study may stop for futility.

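### The Phase I safety gate is worded as no death by Study Day 15, and no supplied text requires DLT status to Study Day 28 before the DMC recommends Phase II

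*Protocol*

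**What the plan says.** **The gate.** Protocol Section 14.10 stops the study and convenes the DMC if any of the 14 Phase I subjects dies by Study Day 15, whatever the cause. It continues: "If no such events have occurred in all 14 subjects, it is deemed safe to proceed to Phase II of the study". The events meant are those deaths. The synopsis, Section 5.1, SAP Section 3 and SAP Section 13.1.1 all make Phase II depend on the stopping rules or on the product being judged safe, together with at least 2 of 14 responders by Day 15.

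**The safety endpoint.** Table 2 in Section 5.4 gives the Phase I primary safety endpoint this timeframe: "DLTs assessed from Study Day 1 through Day 28". Only the futility check is set at Day 15. Section 14.11.1 says of DLT assessment that "AEs will be collected up to Day 28 post first dose of CYNK-001 infusion". The DLT definition in Section 6.3 covers new Grade 4 or 5 events, and Grade 3 or higher allergic reactions, GvHD and cytokine release syndrome (CRS), with the same 28-day horizon.

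**The meeting.** Section 14.11.2 sets the go review as follows: "After Day 15 of the final subject treated in the Phase I portion of the study is complete, DMC will meet". It adds: "Data outputs for review should be provided to the DMC via email at least 2 weeks prior to scheduled meeting".

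**Other routes for DLTs.** Any DLT in the first 3 subjects, or DLTs in 2 of 6, convenes the DMC. SAP Section 3 states: "In Phase I, any DLT finding will be forwarded to the DMC for recommendation, review and confirmation" of whether the MTD has been exceeded, and protocol Section 6.3 says much the same. Under Section 14.11.2, any single DLT up to Day 28 is notified to the DMC Chair within 24 hours of the sponsor learning of it.

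**The concern.** The sentence that defines safe to proceed uses a narrower event (death) and a shorter window (15 days) than the endpoint Phase I was set up to measure. Read literally, a Phase I with several non-fatal DLTs, or with a death on Day 20, meets the wording.

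The DMC's review and recommendation prevent that literal reading from being the whole decision. What remains is timing. The go meeting is anchored to Day 15 of the last subject, and no supplied text says that DLT windows must be closed, or DLT status brought up to Day 28, before the recommendation. Late CRS, GvHD or death in the last few subjects could be missing from the outputs the DMC relies on and reach it only as individual notices.

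The recommendation opens a phase in which up to 36 subjects receive the product. Section 12.6.1 asks for GvHD-related events to be followed for at least 100 days after the last infusion, so the sponsor itself treats delayed toxicity as a real possibility.

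**Working it through.** The plan gives no figure to reproduce here. The check compares timelines and then sizes the gap.

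**1. What each item covers**

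| Item | Event | Horizon | Source |
|---|---|---|---|
| Safe-to-proceed sentence | Death | Day 15 | Protocol 14.10 |
| Futility check | OSCI improvement | Day 15 | Table 2 |
| Primary safety endpoint | DLTs | Day 28 | Table 2 |
| DLT definition and collection | DLTs | Day 28 | 6.3, 14.11.1 |
| DMC go meeting | Safety and efficacy review | After Day 15 of last subject | 14.11.2 |

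**2. The last subject at a Day 15 cut**

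- Unobserved DLT days: 28 − 15 = 13, and 13/28 = 46%.
- Days since an on-schedule third dose (Day 7): 15 − 7 = 8. With the 48-hour delay allowed in Section 6.5 (Day 9): 15 − 9 = 6.
- The same at Day 28: 28 − 7 = 21, or 28 − 9 = 19.

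**3. All 14 subjects**

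Phase I accrual is not stated, so the spacing d between first doses is an assumption. The subject k places before the last has max(0, 13 − k·d) days open. Total DLT follow-up is 14 × 28 = 392 subject-days. The last row uses the SAP's whole-study expectation of 86 subjects in 5 months (5 × 30.4 = 152 days; 152/86 = 1.77 days apart), which may not apply to Phase I.

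| Spacing d | Windows open | Subject-days open | Share of 392 |
|---|---|---|---|
| 13 days or more | 1 (7%) | 13 | 3.3% |
| 7 days | 2 (14%) | 13 + 6 = 19 | 4.8% |
| 3.5 days | 4 (29%) | 13 + 9.5 + 6 + 2.5 = 31 | 7.9% |
| 1.77 days | 8 (57%) | 8 × 13 − 28 × 1.77 ≈ 54.5 | 13.9% |

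**4. Chance that at least one DLT is still to come**

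The documents give no DLT rate. Let p be an assumed risk per subject over Days 16 to 28, spread evenly. With S open subject-days the chance is 1 − (1 − p)^(S/13).

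| p | S = 13 | S = 19 | S = 31 | S = 54.5 |
|---|---|---|---|---|
| 2% | 2% | 3% | 5% | 8% |
| 5% | 5% | 7% | 11% | 19% |
| 10% | 10% | 14% | 22% | 36% |
| 20% | 20% | 28% | 41% | 61% |

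**5. Effect of the two-week lead for outputs**

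- If outputs containing the last subject's Day 15 data go out 14 days ahead, the meeting falls on about Day 15 + 14 = Day 29. Open windows are then max(0, 28 − 29) = 0. The outputs may still stop near Day 15, so the same subject-days can be absent from them.
- If the lead is not kept (the text says should), the meeting can fall while windows are open.

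**6. Do the other routes supply Day 28 status?**

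- They pass on DLTs that have been reported. None asks for confirmation that each subject's window has closed.
- After notice of a single DLT, the Chair may review it and may ask for a meeting; neither is required.
- For subjects 4 to 14, Section 6.3 assesses DLT events through the stopping rules, and in Section 14.10 the rule for those 11 subjects is death. One non-fatal DLT among them does not by itself convene the DMC.
- SAP Section 14.1 plans a table of events meeting the DLT criteria, but SAP Section 4.3 limits everything outside the DMC material to the final analysis, and SAP Section 8 names no DLT output for the DMC.
- Required daily safety calls run to at least the Day 15 visit. In Table 3 the Day 28 visit has a window of ±2 days, so it may not have taken place by a Day 29 meeting.

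**The case against.** The strongest reply is that the quoted sentence is not what actually opens Phase II. The DMC must review cumulative safety and efficacy data and recommend moving forward, and SAP Section 8 leaves it to recommend continuing, de-escalating, stopping or proceeding. A death on Days 16 to 28 is a Grade 5 event and therefore a DLT. DLT findings must be forwarded, the Chair is told of each one within 24 hours of the sponsor being informed, and SAEs are due to Drug Safety within 24 hours. Day 15 is a floor for the meeting, and with the two-week lead every window has closed by about Day 29. The charter, which holds the operating detail, was not supplied.

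Most of this is right, and it limits the severity. A late DLT that has been reported would probably be known to the Chair. What the supplied text still lacks is any requirement that Days 16 to 28 be complete, or their status presented, before the recommendation. The lead time is advisory and says nothing about the data cut.

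Three smaller points also carry weight:

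- The figure of 36 is total Phase II exposure. Moving the decision by 13 days affects far fewer: at the SAP's average rate, 13 × 86/152 ≈ 7.4 randomised and about 3.7 dosed.
- The 100-day GvHD follow-up shows that late toxicity is taken seriously, but it does not single out Day 28 as the right gate. Day 28 is the plan's own DLT horizon.
- The Phase II stop for a death by Day 15, the midpoint DMC review, and the separate DMC recommendation needed for outpatient dosing would all limit harm.

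**Conclusion.** The point holds as a cheap improvement to the plan as written. Section 14.10 equates safety with no death by Day 15, while the Phase I primary safety endpoint is DLTs to Day 28. The plan can be followed exactly and still reach a go recommendation with that endpoint incomplete.

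The firm figure is 13 of 28 DLT days (46%) unobserved for the last subject at a Day 15 cut. The number of open windows rests on assumed spacing: 1 to 4 of 14 (3% to 8% of DLT follow-up) at spacings of 3.5 days or more, and about 8 (14%) at the SAP's whole-study rate. If the two-week lead is kept, no window is open at the meeting, but the same days can be missing from its outputs.

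The charter may already require a Day 28 update. SAP Section 15 reports early closure with 7 subjects dosed in Phase I, so the gate was not reached.

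**What to change.** Replace the safe-to-proceed sentence in Section 14.10 with wording such as:

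> Phase II may open only if none of the 14 subjects has died by Study Day 15 and the DMC recommends proceeding after reviewing all Section 6.3 DLTs, with status updated through Study Day 28 of the last Phase I subject.

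- Match this in the synopsis, Section 5.1, SAP Section 3 and SAP Section 13.1.1.
- In Section 14.11.2, set the go decision on or after Day 28 of the last subject. The Day 15 package can still go out first, followed by a short DLT update.
- Assign the SAP Section 14.1 DLT table to that meeting.
- Keep the automatic stop for a death by Day 15 and the review of the first 3 subjects. No numeric DLT limit is proposed, so DMC judgement is kept.

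**Cost.** No extra subjects or visits, because adverse events are already collected to Day 28. The delay to Phase II is 0 to 13 days:

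- about 0 if the two-week lead already puts the meeting at Day 29 and a brief update is added;
- 28 − 15 = 13 if the meeting would otherwise be held at Day 15;
- 42 − 29 = 13 if a full Day 28 package must have its own two-week lead (28 + 14 = 42).

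The change is a protocol amendment, so it also needs IRB/EC approval under Section 15.3.
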